5.7 Adherence/Compliance

5.7.1 All vaccine will be administered by appropriately trained personnel at each site. Vaccine administration will be documented on the Intervention Administration CRF.

5.7.2 Individuals who receive the Week 0, Week 2, and Week 10 injections will be considered evaluable for the primary endpoint. If subjects receive at least 1 but not all 3 injections, they will still be considered evaluable for secondary endpoints.

6. PHARMACEUTICAL INFORMATION

6.1 MUC1 Vaccine (IND # , NCI, Division of Cancer Prevention)

MUC1 Peptide

The MUC1 peptide is composed of 100 amino acids (aa), representing five 20aa-long tandem repeats of the MUC1 VNTR region: H_2N -(GVTSAPDTRPAPGSTAPPAH)₅-CONH₂. The peptide is synthesized on a rapid multiple peptide synthesizer (Dupont NEN) in a dedicated facility under a strict and fully certified procedure and using reagents with a defined expiration date. The peptide is highly hydrophilic and for testing as well as injection, it is dissolved in sterile saline. The peptide is tested for pyrogenicity and safety in guinea pigs, mice, and rabbits in accordance with an FDA approved protocol in a commercial facility. Once tested negative, it is aliquoted in small freezer vials containing one injection volume (100 mcg lyophilized peptide in 0.05 mL of sterile saline). Two percent of vials are sampled randomly for sterility testing in the University of Pittsburgh Medical center Microbiology Laboratories. Both 7 and 14-day sterility results are recorded. Peptide synthesis procedure, safety, pyrogenicity and sterility are contained in detail in [name] IND application to the FDA cross referenced by NCI, DCP. This peptide and all these procedures have been previously examined and approved by the FDA six times in six different IND applications. For administration as a vaccine, the peptide will be admixed with the POLY-ICLC adjuvant described above and below and injected subcutaneously as described above.

Poly ICLC

Poly-ICLC is supplied by Oncovir in vials containing 1 mL of 2 mg/mL opalescent white suspension. Poly-ICLC is withdrawn from the vial under sterile conditions and is to be administered intramuscularly, subcutaneously or intranasally as supplied. It can also be diluted with normal saline.

Each vial Poly-ICLC will be labeled with the following information:

- Drug Name
- Concentration
- Lot Number
- Date of Manufacture
- Manufacturer
- Investigational Use Statement

Low-dose Poly-ICLC administered IM or SC or intranasally has been well tolerated in clinical trials of patients with brain tumors, other cancers, multiple sclerosis, and in normal volunteers. Multiple additional trials have used it in combination with various cancer or HIV vaccines. The most common adverse events experienced in these studies have been transient discomfort at the injection site and transient malaise. Subcutaneous injection may result in a transient erythematous skin reaction. Preliminary findings from these trials suggest that low-dose Poly-ICLC may be effective in treating various tumors and further study is warranted.

Poly ICLC synthesis, procedure, safety, pyrogenicity, and sterility are contained in detail in the Oncovir IND and DMF to the FDA cross-referenced by NCI, DCP.

Common, Some May Be Serious In 100 people receiving the injection, more than 20 may have:

- Redness at injection site (erythema)
- Pain/soreness at injection site
- · Painful, red swelling at injection site
- Flu-like symptoms, which may include fever chills, headache, fatigue, muscle pain, and joint pain
- Night sweats
- Loss of appetite
- Low albumin blood test result (a type of protein in the blood)
- Fever
- Tiredness

The redness and soreness generally resolve within a few days to a week. Generally, acetaminophen (Tylenol®) is sufficient for pain relief. The flu-like symptoms generally resolve within 12-24 hours. Acetaminophen (Tylenol®) generally helps with these symptoms if they occur.

Occasional, Some May Be Serious In 100 people receiving the injection, 4 to 20 may have:

- Low white blood cell count (cells that fight infections)
- Low platelet count (cells that help the blood clot in order to stop bleeding)
- Anemia (which may cause tiredness, or may require blood transfusion)
- Abnormal liver function test results

Rare, Some May Be Serious In 100 people receiving the injection, 3 or fewer may have:

- · Hives, shortness of breath, or an allergic reaction that is life-threatening
- Immune reaction to his or her own tissue (autoimmune diseases) or if present, may be made worse.

6.3 Availability

MUC1 100mer peptide and Poly-ICLC will be supplied by the University of Pittsburgh and sent to each participating site's research pharmacy upon receipt of a completed CPN Study Agent Order Form. The vaccine injection will be prepared by each participating organization's pharmacy (or other appropriate designated personnel) within 8 hours prior to clinical administration. The dose will be mixed and prepared as per the pharmacy instructions. Study agent will be supplied by and shipped from:

[name]., [name] [contact]; [contact]; E-mail: [contact]

^{*} MUC1 vaccine IB (Edition 2, 15Nov2017) and Hiltonol/Poly-ICLC IB (Edition 14, 25Jan2018)

6.4 Agent Distribution

Agents will only be released by NCI, DCP after documentation of CIRB approval of the DCP-approved protocol and consent is provided to DCP and the collection of all Essential Documents is complete (see DCP website for description of Essential Documents).

The Investigator, or a responsible party designated by the Investigator, must maintain a careful record of the inventory and disposition of all agents using NCI Drug Accountability Record Form (DARF) or comparable institutional form. The investigator or designee is required to maintain adequate records of receipt, dispensing, and final disposition of study agent. Include on receipt record from whom the agent was received and to whom study agent was shipped, date, quantity, and batch or lot number. On dispensing record, note quantities and dates study agent was dispensed to and returned by each participant.

6.5 Agent Accountability

The Investigator, or a responsible party designated by the Investigator, must maintain a careful record of the inventory and disposition of all agents received from DCP using the NCI Drug Accountability Record Form (DARF). The Investigator is required to maintain adequate records of receipt, dispensing and final disposition of study agent. This responsibility will be delegated to the Participating Organization pharmacist. Include on receipt record from whom the agent was received and to whom study agent was shipped, date, quantity and batch or lot number. On dispensing record, note quantities and dates study agent was dispensed to and returned by each participant.

6.6 Packaging and Labeling

The participating organization pharmacy personnel will be required to label the injection supplied for each participant. Each injection should be labeled according to institutional guidelines. The label should define the injection as MUC 1 100mcg/0.05mL w. poly-ICLC 500mcg/0.25mL. The label should also include the date of preparation, the route of administration, and the study name. The label may also include other information, such as the time of expiration, as required by local or state regulations.

6.7 Storage

The MUC-1 vaccine will be stored frozen at-70 to -80° C until mixed for injection. MUC1 Vaccine will be shipped on dry-ice overnight to each site. Participating organizations are required to store the vaccine in a -70 to -80° freezer upon receipt.

Poly-ICLC is stable at room temperature for brief periods (days). It is normally refrigerated at about 40°F (2-8°C) but should not be frozen. Poly-ICLC will be shipped at ambient temperature overnight to each participating site. It is to be stored in the refrigerator upon receipt.

6.8 Pre-Registration and Registration

6.8.1 Participant Pre-Registration

6.8.1.1 To pre-register a participant, the participating site will send the completed, signed, and dated Pre-Registration Eligibility Checklist, to the CPN Registration Office (Email: [contact]; [contact]) to pre-register all participants. The CPN Registration Office will enter the information into the CPN-hosted database. A unique participant identification number (PID) will be assigned. No study-related activities may take place until pre-registration has taken place.

6.8.1.2 At the time of pre-registration, the following will also be verified:

- CIRB (local context subcommittee) approval for the registering institution
- Participant eligibility (including existence of a signed informed consent document)
- Existence of a signed authorization for use and disclosure of protected health information (USA Institutions only)
- Study agent is available and Drug Shipment Authorization has been granted to the registering site
- The following will also be recorded:
 - Participant has/has not given permission for blood samples to be collected and that these samples and related information may be used for optional laboratory studies.
 - Participant has/has not given permission for the study doctors to contact them or their physician to see if they wish to learn about the results from the optional studies.
 - Participant has/has not given permission for blood samples and related information to be kept in a Biobank for use in future health research.
 - Participant has/has not given permission for information from their alcohol and tobacco use assessments to be used for future health research
 - Participant has/has not given permission to send blood sample(s) and related information to researchers at outside institutions.
 - Participant has/has not given permission to their study doctors (or their representative) to contact them to see if they wish to participate in research in the future.
- 6.8.1.3 Baseline (screening) evaluations must be completed within the guidelines specified on the Schedule of Events (See Section 7.1).
- 6.8.1.4 Registration Office personnel will automatically register participants separately to the translational components of the study (See Section 13).

6.8.2 Registration

- 6.8.2.1 To register a participant, the participating site will send the completed, signed, and dated Registration Eligibility Checklist to the CPN Registration Office (Email: [contact]; [contact]). The CPN Registration Office will enter the information into the CPN-hosted database. For randomization details, see Section 13.2.
- 6.8.2.2 Intervention on this protocol must commence at a CPN institution under the supervision of a CPN clinician.

6.8.2.3 Intervention cannot begin prior to Registration and must begin ≤ 14 days after Registration.

6.8.2.4 Descriptive Factors:

- Participating organization: University of Pittsburgh versus Mayo Clinic
- Gender: Male versus female
- Smoking status: Current versus former

6.9 Blinding and Unblinding Methods

Not applicable

6.10 Agent Destruction/Disposal

At the completion of investigation or after completion of the site pharmacy final close out visit report by the CPN Compliance Coordinator, all unused study agent will be returned to the University of Pittsburgh. The University of Pittsburgh will supply instructions, shipping supplies, shipping bills, and other items necessary for the return shipment.

7. CLINICAL EVALUATIONS AND PROCEDURES

7.1 Schedule of Events

Study Visit/Event	Pre- Registration	Screening	Registration/ Day 0	Week 2 (+/- 4 days)	Week 4 (+/- 4 days)	Week 10 (+/- 4 days)	Week 12 (+/- 4 days)	Weeks 16 and 20 (+/- 4 days)	Week 24 (or early termination, +/- 7 days)	Week 28 (+/- 14 days)
Informed consent	X									
Physical exam		Х							Х	
Vital signs ¹		Χ	Х	Х		Х			X	
Med/Surg history		Х								
Alcohol and Tobacco Use Assessment		Х							х	
Baseline symptoms		Х								
Con Meds		X	X	Х	Х	X	X	X	X	
Hematology tests ²		X		Χ	Х	Х	X		X	
Blood chemistry ³		X		X	X	X	X		X	
Urine cotinine		Χ					X		X	
Pulmonary function ⁴		Х							Х	
Immunological testing ⁵		Х		X	X		x		х	
Blood testing for exploratory endpoints ⁶		Х							х	
Pregnancy test, urine, if applicable		Х	X	Х		x				
Vaccine administration ⁷			Х	Х		x				
AE assessment			Х	Χ	Х	Х	Х	Х	Х	
Phone call ⁸								Х		X
WIWI Questionnaire									х	

- 1. Vital signs include height (screening only), weight, temperature, blood pressure, heart rate, respiratory rate.
- 2. Hematology testing (evaluated at local labs) includes CBC with 5-part differential and platelets.
- 3. Blood chemistry tests (evaluated at local labs) include: potassium, sodium, chloride, bicarbonate, creatinine, serum glucose, BUN, total bilirubin, alkaline phosphatase, AST/SGOT, ALT/SGPT, uric acid, amylase, lipase, and albumin. At the screening, Week 4, and Week 24 visits only, blood testing will also include antinuclear antibody (ANA). Optional research blood will be collected at screening and Week 24, if participant consent is provided.
- 4. Testing (evaluated locally) includes spirometry, including graphic record, total and timed vital capacity, expiratory flow rate measurement, with or without maximal voluntary ventilation, and pulmonary diffusing capacity.
- 5. Immunological testing for antibody responses to MUC1 (See Section 9.1).
- 6. All blood testing for secondary and exploratory endpoints will utilize plasma remaining after the immunological studies are complete with the exception of high sensitivity C-reactive protein (hsCRP). For individuals accrued prior to protocol Amendment 2, levels of hsCRP will be tested at baseline and Week 24 using frozen plasma remaining from the blood draw for immunological studies (See footnote #5 above). Beginning with Amendment 2, one extra blood specimen will be collected, processed into serum, and stored until the end of the study for hsCRP.
- 7. Where applicable, blood draws and AE assessments will precede vaccine administration (See Section 7.4).
- 8. If any adverse events have not resolved at the time of the Week 24 visit, an optional follow up phone call may take place at Week 28 (+/- 7 days).

7.2 Baseline Testing/Pre-study Evaluation

After participants have been informed about the study and have signed the informed consent document, they will be pre-registered and assigned a unique participant identification number (PID).

They will then undergo initial screening tests and procedures. The order in which these tests and procedures is conducted is flexible within the designated study timelines and should be consistent with good clinical practice and institutional policies and procedures. These tests and procedures include a physical exam, documentation of medical/surgical history, alcohol and tobacco use assessments, review of clinical CT imaging, and documentation of any existing baseline symptoms, allergies, concomitant medications, and baseline blood tests. Baseline blood tests include ANA, CBC with 5-part differential and platelets, potassium, sodium, chloride, bicarbonate, creatinine, serum glucose, BUN, total bilirubin, alkaline phosphatase, uric acid, AST/SGOT, ALT/SGPT, albumin, amylase, lipase, and an optional additional specimen for future research. Blood will also be drawn at baseline/screening for the immune assays and exploratory endpoints. A urine cotinine test will be performed. Pulmonary function testing includes spirometry, including graphic record, total and timed vital capacity, expiratory flow rate measurement, with or without maximal voluntary ventilation and pulmonary diffusing capacity. A urine pregnancy test will be administered, if applicable.

If participants are eligible and willing to participate, they will be registered to the study.

7.3 Evaluation During Study Intervention

Vaccine will be administered at Weeks 0, 2, and 10. Participants will be monitored for at least 30 minutes after each injection for possible emergent side effects.

Prior to vaccine administration:

- Females of childbearing potential will be required to document negative pregnancy test.
- Blood will be drawn for safety and/or immune response, as applicable (See Section 7.1 and see below).
- Adverse events and concomitant medications will be assessed (See Section 11.1 for details).
- Vital signs will be evaluated (temperature, blood pressure, heart and respiratory rates, and weight)
- Blood testing results will be reviewed by the treating physician for clinical significance and possible indications of toxicity.

Immune response will be tested at Weeks 2, 4, and 12. A repeat ANA titer will be drawn at Week 4. Blood tests to monitor toxicity will be conducted at Weeks 2, 4, 10, and 12. Urine cotinine will be monitored at Week 12.

Adverse events will be evaluated during all contacts with the participants, with emphasis on AE evaluation two weeks after each injection (See Section 11.1 for details). Possible adverse events and concomitant medication information will be captured by telephone at Weeks 16 and 20.

7.4 Evaluation at Completion of Study Intervention (or early termination)

The post-intervention evaluation will take place at Week 24 (+/- 7 days). The order in which these tests and procedures is conducted is flexible within the designated study timelines and should be consistent with good clinical practice and institutional policies and procedures. These tests and procedures include a physical exam, review of adverse events, and concomitant medications, alcohol and tobacco use follow-up assessments, and blood tests. Blood tests include CBC with 5-part differential and platelets, potassium, sodium, chloride, bicarbonate, creatinine, serum glucose, BUN, total bilirubin, alkaline phosphatase, uric acid, AST/SGOT, ALT/SGPT, albumin, amylase, lipase, and ANA. Blood will also be drawn for the immune assays and exploratory endpoints. An optional additional blood specimen will be collected for future research, if consent was provided. A urine cotinine test will be performed. Pulmonary function testing includes spirometry, including graphic record, total and timed vital capacity, expiratory flow rate measurement, with or without maximal voluntary ventilation, and pulmonary diffusing capacity. The Was It Worth It (WIWI) Questionnaire will also be administered. If the participant provides consent, the data from this questionnaire will be included in the central Quality of Life database (along with demographic information) that is accessible to non-study investigators after CIRB approval.

7.5 Post-intervention Follow-up Period

If any adverse events have not resolved at the time of the Week 24 visit, a follow up phone call may take place at Week 28 (+/- 14 days). Concomitant medications will be recorded. Adverse events will be followed according to institutional standards of good clinical practice.

7.6 Methods for Clinical Procedures

See Section 5.2 for vaccine preparation and administration procedures.

8. CRITERIA FOR EVALUATION AND ENDPOINT DEFINITION

8.1 Primary Endpoint

See Section 13.4.

8.2 Secondary Endpoints

See Section 13.5.

8.3 Off-Agent Criteria

Participants may stop taking the study agent due to: completion of the planned intervention period, development and/or continuation of an adverse event or serious adverse event, inadequate agent supply, noncompliance, use of concomitant medications, medical contraindication, refusal, ineligibility (see Section 8.4), major treatment violation (see Section 8.4) or alternative treatment. Participants will continue to be followed, if possible, for safety according to the intended schedule of events (see Section 7).

Participants discontinuing the planned intervention prematurely will be encouraged to complete the Post-Intervention Evaluation tests and procedures as appropriate (if participant does not refuse, is not lost to follow-up, or unless it is clinically contraindicated). See Section 8.4 for further details as to data submission for participants deemed Ineligible after starting treatment or classified as a Major Treatment Violation (i.e., protocol requirements regarding intervention during the first week post-registration were severely violated). In such cases, all data and all on-study materials, collected up until the point of confirmation of ineligibility or major violation status must be submitted.

8.4 Off-Study Criteria

Participants may go "Off-Study" for the following reasons: development or continuation of an adverse event or serious adverse event, death, lost to follow-up, participant withdrawal, physician decision, protocol violation, completion of study, or other (with detailed comments provided). Reason(s) will be noted in the participant's research records, with the primary reason clearly identified. The participant will be classified as (Off Study/Off Agent). Data submission and follow-up after participants are determined to be a screen failure or "Off-Study/Off-Agent" for specific situations is noted below:

Ineligible: A registered participant is deemed ineligible if the participant does not satisfy each and every eligibility criterion for study entry.

- If participants received study intervention, on-study materials and all data up until the point of confirmation of ineligibility will be submitted.
- If participants did not receive study intervention, on-study materials must be submitted. No further data submission is necessary. No follow-up is required.

Major Treatment Violation: A registered participant is deemed as being in major treatment violation by the coordinating center, if the participant's very first treatment/intervention administration is so grossly administered in error, that the participant's data can no longer be used for the primary endpoint. These cases are typically rare.

• On-study material and all data up until the point of confirmation of a major violation must be submitted.

Cancel: A registered participant is deemed a cancel if he/she refuses the study before any study intervention is given.

• On-study material must be submitted. No further data submission is necessary. No follow-up is required.

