Safety primary endpoint: AEs and toxicities will be closely monitored for up to 24 weeks after participants receive the first dose of the MUC1 vaccine. All registered and treated participants will be evaluable for adverse events (AEs) from the time of their first dose of the vaccine. To evaluate the AE profile for this treatment, the maximum grade for each type of adverse event will be recorded for each participant and frequency tables will be reviewed to determine the overall patterns. In addition, the number and severity of adverse events will be tabulated and summarized across all grades. Grade 2+ adverse events will be similarly described and summarized separately. As per NCI CTC Version 4.0, toxicities are defined as adverse events that are classified as either possibly, probably, or definitely related to the interventional agent. Overall toxicity incidence, as well as toxicity profiles will be explored and summarized. Frequency distributions, graphical techniques, and other descriptive measures will form the basis of these analyses. In addition, we will review all adverse event data that are graded as 3, 4, or 5 and classified as either "unrelated or unlikely to be related" to the study intervention in the event of an actual relationship developing.

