13.6 Reporting and Exclusions

All registered participants who start treatment and complete both the baseline and 12-week post-baseline evaluation will be evaluable for the 12-week immunogenicity response primary endpoint using the modified intent-to-treat principle, as long as they received the Week 0, Week 2, and Week 10

injections (See Section 5.6 for delays in vaccine administration that are considered allowable and will not impact evaluability for the primary endpoint). We plan to over-accrue by about 20% overall to ensure an adequate sample size in the primary analysis cohort. There will be no imputation for missing data. A summary and listing of all major protocol violations will be provided. All details will be given in the final study report and/or manuscript. Participants lost to follow-up will be censored on the last date of assessment (or contact) and as appropriate for analyses that are dependent upon length of study participation. All eligible participants who start treatment will be evaluable for the safety

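### Sections 8.3 and 8.4 require data only up to confirmation for vaccinated participants found ineligible or in major treatment violation, so later non-serious safety data for a co-primary endpoint need not be submitted

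*Combined protocol and SAP*

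**What the plan says.** Two sections set the data duty for participants who were vaccinated and later found ineligible or in major treatment violation.

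- Section 8.4, ineligible after vaccination: "If participants received study intervention, on-study materials and all data up until the point of confirmation of ineligibility will be submitted".
- Section 8.4, major treatment violation: "On-study material and all data up until the point of confirmation of a major violation must be submitted".
- Section 8.3, both groups together: "all data and all on-study materials, collected up until the point of confirmation of ineligibility or major violation status must be submitted".

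Other sections call for full safety data.

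- Section 8.3 lists ineligibility and major treatment violation among the off-agent reasons and then states: "Participants will continue to be followed, if possible, for safety according to the intended schedule of events (see Section 7".
- Section 11.1.1 requires all AEs after consent and baseline to be entered on the AE form, with no exception for these participants.
- Section 13.4, on the safety primary endpoint: "AEs and toxicities will be closely monitored for up to 24 weeks after participants receive the first dose of the MUC1 vaccine". On who counts: "All registered and treated participants will be evaluable for adverse events (AEs) from the time of their first dose of the vaccine".

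Section 13.6 gives a different safety set: "All eligible participants who start treatment will be evaluable for the safety". That sentence is incomplete in the text available.

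**The concern.** Safety through Week 24 is one of two co-primary endpoints. A site that confirms a vaccinated participant as ineligible will look to Section 8.4, because Section 8.3 refers to it for data submission in exactly these cases. Section 8.4 asks for nothing after confirmation, so records may stop on an administrative date although the participant is still being seen.

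The participants affected are few but informative. One group should not have been vaccinated under the eligibility criteria, which include known autoimmune disease and an ANA titer above 1:160 as exclusions. The other group received a first dose grossly in error. Late immune and lung-function data matter most for such exposures.

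The definition of a major violation adds to the problem. It turns on whether data can still be used for the primary endpoint, as if there were only one. Data that are useless for the Week 12 titer ratio can be fully usable for safety.

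**Working it through.** No stated sample size, power or alpha is involved, so there is no plan figure to reproduce. The check has three parts.

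**1. What falls after the cut-off.** Section 7.1 schedules blood counts and chemistry at Weeks 2, 4, 10, 12 and 24, ANA at Weeks 4 and 24 after baseline, and spirometry at Week 24 only. For any confirmation date before the Week 24 visit:

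| Item | Submission required by 8.3/8.4 | Called for elsewhere |
|---|---|---|
| Non-serious AEs after confirmation | No | Yes: 11.1.1, 13.4 |
| Remaining ANA and laboratory results | No | Yes: 7.1, through 8.3 follow-up |
| Week 24 spirometry, with its own AE definition in Section 11 | No | Yes: 7.1, 11 |
| SAEs | Reported separately | Yes: 11.2 |

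Elsewhere the plan provides for follow-up after vaccination stops: Sections 5.4 and 5.6 keep participants who go off agent for other reasons on per-protocol follow-up. The cut-off at confirmation is specific to these two groups.

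**2. Effect on the AE table.** Section 13.4 tabulates the maximum grade per participant, without person-time. Section 13.6 allows no imputation and mentions censoring only for participants lost to follow-up. The direction of any error depends on which safety set applies:

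- Under 13.4, a truncated participant stays in the denominator and appears to have no later event, so event rates are biased downward. Each such participant is 1/50 = 2% of the planned 50.
- Under 13.6 read literally, an ineligible participant leaves numerator and denominator altogether, including events before confirmation.

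**3. Effect on the stopping rule.** Section 13.7 suspends accrual at 2 of the first 10 treated participants with an at least possibly related grade 3 or higher AE, or at 20% of all participants beyond 10. Assumptions, since the documents give no rates: true event probability p = 0.10 to 0.30, the same for everyone; one of the first 10 truncated; share f = 0.5 to 1 of that participant's event risk unobserved.

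With full data, P(at least 2 of 10) = 1 − (1−p)^10 − 10p(1−p)^9.

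The lost event matters only when exactly one of the other nine has an event, so the loss is f × p × 9p(1−p)^8 = f × 9p²(1−p)^8.

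| p | Full data | Loss at f = 1 | Truncated, f = 0.5 | Truncated, f = 1 |
|---|---|---|---|---|
| 0.10 | 0.264 | 0.09 × 0.4305 = 0.039 | 0.245 | 0.225 |
| 0.20 | 0.624 | 0.36 × 0.1678 = 0.060 | 0.594 | 0.564 |
| 0.30 | 0.851 | 0.81 × 0.0576 = 0.047 | 0.827 | 0.804 |

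The loss is about 2 to 6 points. The expression p²(1−p)^8 peaks where 2(1−p) = 8p, that is at p = 0.20, so 6 points is the maximum for one participant under the common-rate assumption.

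With three truncated participants among the first 10 and all their risk unobserved, the probabilities fall to 0.150, 0.423 and 0.671. At a single look at 50 participants (10 events needed), one to three truncated participants move the probability from 0.556 to between 0.542 and 0.471 at p = 0.20, and from 0.960 to between 0.956 and 0.933 at p = 0.30.

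**The case against.** A reader might infer that AEs after confirmation can never reach the safety analysis or the stopping rule. The documents do not support that. Sections 8.3 and 8.4 say what must be submitted; they do not bar anything further. Where the protocol wants to end the duty it says so: "No further data submission is necessary. No follow-up is required". That wording is attached only to ineligible participants who were never vaccinated and to those who cancel before any injection. Section 8.3 also encourages early discontinuers to complete the post-intervention evaluation. Section 11.1.1 has no exception, and Section 13.7 acts on events observed, with discretion to suspend accrual before the rule is crossed. All of this stands, and it limits the point to data that may be lost. It does not remove the conflict: being followed is not the same as having data submitted, and the follow-up is qualified as where possible.

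Section 11.2 sends deaths, life-threatening events and hospitalizations to the medical monitor within 24 hours, so the gap in the stopping rule is largely confined to related, non-serious grade 3 events. That also stands.

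A reader might also take one missing event as turning 2 of 10 into 1 of 10. That needs an affected participant among the first 10, an unreported qualifying event after confirmation and exactly one other event. The probabilities above are the fair measure. Likewise, a figure of 22 of 24 weeks (92%) lost would rest on an assumed Week 2 confirmation and would count calendar time, not risk: Section 6.2 says local and flu-like reactions generally resolve within days.

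Earlier experience with this vaccine and schedule (Sections 2.2 and 6.2) showed no AE above grade 1 in 40 participants, and ANA is checked before registration. Both make a consequential case less likely. Finally, the master data management and safety monitoring plans cited in Section 12 may say more, but they are not available here.

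**Conclusion.** The inconsistency is real and its practical effect is small. The protocol requires less data from two groups of vaccinated participants than its own co-primary safety endpoint needs, so non-serious events and scheduled safety results after confirmation may be missing.

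The number affected is unknown: no rate of ineligibility found after registration is given, and major violations are described as rare. The 2 to 6 point loss for one participant among the first 10 rests on the assumed event rates, on half to all of that participant's risk being unobserved, and on a common risk. If the affected participant's own risk were higher, the loss would rise in proportion.

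Downward bias in event rates should not be taken as settled. It follows under Section 13.4, but under Section 13.6 the ineligible participants would be excluded entirely. That conflict has to be resolved together with the cut-off, since settling the safety set alone would not recover data that were never submitted.

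**What to change.** 1. In Sections 8.3 and 8.4, for anyone who received at least one injection, require AE, laboratory and Week 24 safety data to be submitted through Week 24, subject to the participant's continued consent.
2. Keep the short submission rule only for participants who were never vaccinated.
3. In the major-violation definition in Section 8.4, refer to the immunogenicity primary endpoint specifically.
4. Align Section 13.6 with the all-treated safety set of Section 13.4, and use that set for the Section 13.7 count as well.

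The cost is amendment wording and a few extra CRF pages for a small number of participants. No new visits are needed, because Section 8.3 already intends the follow-up.
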